### III.C3. Aim 3 Measurement/Instrumentation

Exhaled CO levels will be used to determine eligibility and CO boost (post- minus pre-smoking levels) from WP smoking using a handheld electrochemical sensor. The primary quantitative outcomes will be exhaled breath CO and plasma nicotine boost (post- subtracted from pre-smoking levels), puffing topography, spirometry measures [e.g., forced vital capacity (FVC), forced expiratory volume in 1 second (FEV1), FEV1/FVC, peak expiratory flow (PEF) and forced expiratory flow at 25-75% of FVC; and height and weight will also be assessed to calculate expected spirometry measures for participants. In addition, data will be collected electronically on participants' demographic characteristics, tobacco use history, nicotine dependence (Hooked on Nicotine Checklist, and Lebanese WP Dependence Scale), general harm and specific health risk perceptions, and subjective effects, including Direct Effects of Tobacco scale, Direct Effects of Nicotine scale, and Questionnaire for Urges to Smoke.

The primary qualitative outcomes will be verbal and non-verbal communication regarding the WP smoking experience and flavors perception. To determine the relative intensity of specific flavors, e.g., sweetness, we will use the general version of the Labeled Magnitude Scale (gLMS), to obtain data that would permit ratio comparisons of perceived sensation magnitudes. To assess the degree of liking or disliking of flavors, we will use the Labeled Hedonic Scale (LHS) to collect ratio-level data on the magnitude of liking and disliking of sensation. Other themes that emerge from the discussions will also be coded.

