**Spirometry.** Before and after smoking at each clinic visit, subjects will be asked to take a deep breath and then instructed to exhale forcefully into a handheld spirometer [NDD EasyOne Air Spirometer (NDD Medical Technologies, Andover, MA), or similar spirometer] according to American Thoracic Society Guidelines. This maneuver will be repeated up to 5 times in order to

ensure reproducible results. This non-invasive procedure will take up to 15 minutes to perform. Participants' height and weight will also be measured to calculate their expected spirometry measures as thresholds to use for determining potential impairment in lung function.

Safe Departure and Remuneration. At the end of each clinic session, research assistants will assess each of the participants for safe departure using a standardized checklist. An example checklist is provided in Appendix C. Visits 2-4 will be similar to the first visit, but the tobacco and use history data collection and the urine pregnancy test (women only) will not be repeated. Participants will receive \$50 for each laboratory visit and a bonus payment of \$50 for completing all four visits, for a total of \$250 at the conclusion of the last laboratory visit.

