## VII. Data Analysis

### VII.1 Analysis Plan

The main research questions from the four Aims in the proposed study have the same structure for data analysis. That is, there are differences attributable to the four tobaccos in the means of the outcome measures of interest. All relevant outcome variables will be first examined with exploratory/descriptive statistical analyses that focus on describing and understanding patterns and distributions for all relevant measures (e.g., tobacco chemical content, mainstream smoke constituents, spirometry measures, topography measures, psychophysical ratings) by the four tobaccos. We will identify any potential outliers, assess distributional assumptions, and apply appropriate transformations to the outcome variables (e.g., log-transformation) if the normality assumption is violated.

For each of the four aims, the following pairwise comparisons will be performed:

$$H0i j: \mu_i = \mu_j \text{ vs. } H1i j: \mu_i \neq \mu_j$$

where  $\mu_i$  = mean target outcome for tobacco type i, and  $\mu_j$  = mean target outcome for tobacco type j. In Aims 1, 2, and 4, the data will be analyzed using one-way ANOVA models for independent outcome data and Tukey's method will be used to control type-I error rate across the six multiple comparisons. A different analysis strategy will be used in Aim 3 due to the clustered study design: participants will complete four different smoking sessions. Thus, in order to account for the hierarchical design, the data in Aim 3 will be analyzed using linear mixed models containing random subject effects. Since linear mixed models allow for incomplete data (e.g.,

due to dropout), data from all completed smoking sessions will be used in the analysis. As in the other aims, Tukey's method will be used to adjust for multiple comparisons of the tobacco treatments in Aim 3. In addition, for Aim 3, we will use linear mixed models to examine the relationships between the perceived sensory intensity ratings and the liking/disliking ratings for a given tobacco preparation.

Integrating results from Aims 1, 2 and 4 with Aim 3 of the study, the absence or presence, or exposure level of certain HPHCs and other chemical compounds across the different tobacco preparations will be mapped with the data on perceived sensory intensity such as sweetness and liking/disliking ratings.

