## VII.2. Sample Size Justification.

Since Aims 1, 2, and 4 do not involve human subjects, we expect low variability across replicates. Thus, assuming a somewhat conservative coefficient of variation (CV) of 20% and log-normal outcomes, a total of **4 replicates per tobacco preparation** will provide 80% power to detect a two-fold change in the geometric means of two groups at a conservative two-sided Bonferroni-corrected type-I error rate of 0.0083.

Our sample size for Aim 3 was selected to ensure that we have adequate power to detect moderate effect sizes in our comparisons of topography outcomes. We made the following assumptions for the power analysis:

- Based on the intravariability data analysis for the RWP, correlation coefficients within subjects ( $r$ ) were assumed to be 0.6, 0.7 or 0.8.
- Small, medium, and large effect sizes ( $d$ ) of 0.2, 0.5, and 0.8 standard deviations.
- A two-sided, Bonferroni corrected type-I error rate of 0.0083.

Our power analysis, summarized in Table VII-5, revealed that a sample size of 43 subjects will provide over 80% power to detect a moderate effect size unless the within pair correlation is high (0.2 or 0.3) and the within participant correlation is modest (0.6). However, since this power analysis assumes complete follow-up, we will recruit **60 participants** to account for a possible attrition rate of 20%, and ensure the Latin square ordering is balanced across the four tobacco types.

Table VII.5. Estimated % power to for pairwise comparisons of tobacco preparations based N = 25 pairs (50 subjects).

$r$	$\rho$	Power		
		$d=0.2$	$d=0.5$	$d=0.8$
0.6	0.1	0.108	0.803	0.998
	0.2	0.097	0.759	0.996
	0.3	0.088	0.717	0.994
0.7	0.1	0.153	0.918	> 0.999
	0.2	0.138	0.889	> 0.999
	0.3	0.125	0.857	0.999
0.8	0.1	0.255	0.989	>0.999
	0.2	0.228	0.981	>0.999
	0.3	0.207	0.971	>0.999

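### The plan does not define the spirometry outcome and gives the same-visit pre-smoking value no role in the Aim 3 model; adjusting for it could gain precision at almost no cost

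*Combined protocol and SAP*

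**What the plan says.** Section IV schedules spirometry on both sides of each smoking session, in the session narrative and again in the Spirometry paragraph: "Before and after smoking at each clinic visit, subjects will be asked to take a deep breath". A participant who completes the study therefore supplies four pre/post pairs.

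Section III.C3 lists the primary quantitative outcomes of Aim 3. Exhaled CO and plasma nicotine are defined as a boost, that is, a difference between the two time points. The list then moves on without a similar definition for lung function: "post- subtracted from pre-smoking levels), puffing topography, spirometry measures". FVC, FEV1, FEV1/FVC, PEF and mid-range expiratory flow are named as measures only.

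Section VII.1 gives one generic analysis for every Aim 3 outcome: "the data in Aim 3 will be analyzed using linear mixed models containing random subject effects". The hypotheses compare the "mean target outcome for tobacco type i" with that for type j, with Tukey adjustment over the six pairs. The target outcome is not defined for spirometry. No baseline covariate and no pre/post time factor is named.

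**The concern.** The objective for lung function is the acute effect of smoking each tobacco. A participant's lung function also varies from day to day, and the test taken just before smoking records that day's level. The random subject effect removes stable differences between people but not this visit-to-visit component. If the post-smoking value is analysed alone, the component stays in the error term of every tobacco contrast, although the data to remove part of it are already being collected.

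Two things are at stake. One is precision on a listed primary outcome that the sample-size section does not cover, since section VII.2 is built on topography. The other is prespecification: post value, change, and both time points together all fit the present text, for five measures, and the choice could be made after the data are seen.

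**Working it through.** **The plan's own figure.** Section VII.2 uses an error rate described as "A two-sided, Bonferroni corrected type-I error rate of 0.0083", effects of "0.2, 0.5, and 0.8 standard deviations", and within-subject correlations r that "were assumed to be 0.6, 0.7 or 0.8". For a paired comparison by normal approximation,

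power = Φ( d / √[2(1 − r)(1 + ρ)/n] − z ), with z = 2.64 for 0.0083 two-sided.

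At d = 0.5, r = 0.6, ρ = 0.1, n = 43: √(0.88/43) = 0.143; 0.5/0.143 = 3.495; 3.495 − 2.640 = 0.855; power 0.804, against 0.803 in Table VII.5. All 27 cells reproduce with n = 43, to within 0.0013. With the 50 subjects in the table title the same cell would be 0.871; that mismatch is separate from this point. The table concerns topography and has no pre-smoking term.

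**Variance of a tobacco contrast for spirometry.** Let σ² be the within-participant, between-visit variance of the post-smoking value, and p the correlation of pre- and post-smoking deviations within participant and visit. Stable differences between people are already removed by the random effect, so p is not the raw pre–post correlation across people. With equal pre and post variances, relative to post-only:

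- post-only: 1
- change score: 2(1 − p)
- pre-smoking value as covariate: 1 − p²
- covariate relative to change score: (1 − p²)/[2(1 − p)] = (1 + p)/2

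| p (assumed) | Covariate vs post-only | Change vs post-only | Covariate vs change |
|---|---|---|---|
| 0 | 1.00 | 2.00 | 0.50 |
| 0.3 | 0.91 | 1.40 | 0.65 |
| 0.5 | 0.75 | 1.00 | 0.75 |
| 0.7 | 0.51 | 0.60 | 0.85 |
| 0.8 | 0.36 | 0.40 | 0.90 |

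Apart from the degrees of freedom, the covariate is never worse than either alternative: 1 − p² ≤ 1, and 2(1 − p) − (1 − p²) = (1 − p)² ≥ 0. The change score is worse than post-only when p is below 0.5.

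**Standard errors.** Relative to the covariate model, post-only inflates the standard error by 1/√(1 − p²): 0%, 5%, 15%, 40% and 67% at the five values of p.

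**Check by simulation** (50 participants, four visits). Covariate-to-post-only variance ratios were 1.01, 0.93, 0.76 and 0.49 at p = 0, 0.3, 0.5 and 0.7, in agreement with 1 − p².

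**Illustration in power.** Take d = 0.5, n = 43, ρ = 0, and borrow r = 0.6 from the topography assumptions, since none is given for spirometry. Post-only: √(0.80/43) = 0.136; 0.5/0.136 = 3.666; power 0.848. Dividing 3.666 by the square root of the variance factor gives:

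- covariate: 0.886, 0.944 and 0.994 at p = 0.3, 0.5 and 0.7
- change score: 0.677, 0.848 and 0.982

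At r = 0.8 post-only power is already 0.995, so there is little left to gain for an effect of that size.

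**The case against.** The strongest reply is that silence is not exclusion. A reader might infer that the plan discards the pre-smoking value, but no section says so. The VII.1 sentence is a sketch: it does not name the tobacco fixed effect either, although the pairwise comparisons require one. A change score parallel to the CO and nicotine boost would fit the text, particularly as the stated interest is in acute effects. This stands, and it is why the point concerns an undefined outcome and an unassigned covariate. If a change score is what the investigators intend, the gain from adjustment is the smaller one at high p: 15% of variance at 0.7 and 10% at 0.8.

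Second, the size is unknown. The relevant p is what remains after the random subject effect, and the documents do not report it. Showing only values from 0.5 upwards would flatter the case; at p = 0 there is no gain over post-only, and at 0.3 it is 9% of variance. This also stands.

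Third, little else depends on it. The tobacco sequence is randomised, the Aim 3 hypotheses include none on spirometry, and the sample size rests on topography. All true. It limits the consequence to precision and prespecification, but it is no reason to leave a listed primary outcome undefined when the remedy is so cheap.

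A reader might also extend the argument to CO and nicotine. The documents do not support that: the boost is their declared outcome, pre-smoking levels are already restricted by the abstinence requirement and the 10 ppm CO limit, and no figures show a gain there.

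**Conclusion.** The point holds as one of specification and efficiency. The spirometry outcome is not defined, and a pre-smoking value collected at every visit has no stated place in the model. It would be wrong to infer that the tobacco contrasts are biased; under the randomised sequence they are not, whether the post value, the change or the adjusted post value is used.

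Covariate adjustment reduces the variance of a contrast by somewhere between nothing and 64% relative to post-only over p = 0 to 0.8, and by 50% down to 10% relative to a change score over the same range. These figures assume a common p across visits and tobaccos; those involving the change score also assume equal pre and post variances. Which end applies cannot be settled from the documents. The ordering can: apart from the degrees of freedom spent, adjustment does at least as well as either alternative, whereas a change score chosen by analogy with the boost could do worse than ignoring the pre-smoking value. A post-only model would also leave the pre-to-post lung effect itself undescribed.

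**What to change.** In section VII.1, state that each spirometry measure is analysed as the post-smoking value in the linear mixed model, with:

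- tobacco as a fixed effect
- a random participant effect
- the visit's pre-smoking value, as a deviation from that participant's mean pre-smoking value
- the participant's mean pre-smoking value

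The split keeps the between-person slope from distorting the within-visit adjustment. Report the pre-to-post change for each tobacco descriptively. In section III.C3, add the matching outcome definition. Keep the CO and nicotine boosts as declared.

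The cost is about two covariate degrees of freedom, small against up to 50 × 4 = 200 sessions in the complete data sets that the protocol aims for. No new measurement, visit or change to the recruitment target of 60 is needed. The wording should be settled before the spirometry data are examined by tobacco.

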## IV. Detailed Study Procedures for the Human Study (Aim 3)

Study subjects will participate in a series of 4 laboratory sessions, each visit separated by at least a week, in which they smoke one of 4 tobacco preparations (blinded) using the RWP2, shown in Figure II.1, in a randomly assigned sequence, using the block randomization method. Smoking sessions will be carefully standardized: they will take place in a controlled setting, individual roomsdesignated for smoking research with sufficient ventilation rate at the Center for Tobacco

Research) within one hour of the same time-of-day after overnight nicotine abstinence ( $\geq 8$  hours, exhaled CO  $\leq 10$  ppm^173).

Research staff will light and add the charcoal and record tobacco and charcoal weights. The research-grade waterpipes will be prepared by the laboratory staff, and participants will smoke ad lib to satiation. Participants will be limited to one bowl (15 g) of tobacco and one quick-light charcoal (~10 g).

Prior to the start of the first laboratory visit, a research assistant will explain the study to the participant and answer any questions they may have. The participants will give an exhaled breath sample into the handheld CO monitor to determine if they are eligible to participate in the laboratory smoking session. If the participant's exhaled CO concentration is less than or equal to 10 ppm) they are deemed eligible to participate further, and will be asked to read the informed consent form. Once all participant questions have been answered, the participants will each be asked to sign their consent to participate in the study. Each female participant of child-bearing age will be asked to provide a urine sample for use in conjunction with a "dip-stick" pregnancy test to determine participation eligibility. Female participants with a negative urine pregnancy will be eligible to participate if they provide written agreement (via signing the consent form) to use reliable contraception throughout their participation in the study.

Each participant will then be asked to provide a pre-smoking blood sample by venipuncture. If the phlebotomist is unable to take a sufficient blood sample (10 mL) from the participant, the participant will be deemed ineligible to participate further in the study. Participants will then answer demographic and tobacco use questions.

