## **Adverse Events**

Adverse events will be assessed by study staff at each follow-up visit via participant self-report and managed immediately. All adverse events will be reported to the OSU IRB. We will monitor for risk of smoking waterpipe by screening participants for general medical precautions (pregnancy, respiratory and cardiovascular disease). Participants will be given contact numbers of study personnel and Co-PD/PIs [name] and [name]. Any adverse events, breaks of confidentiality, or any other data or safety issues that arise will be discussed immediately between study personnel and the Co-PD/PIs.

Co-PD/PI [name] will be responsible for completing an Adverse Events Form should an event occur. She will report Serious Adverse Events to the OSU IRB within 24 hours of having received notice of the event. She will gather any information needed to investigate the event and to determine subsequent action. Any subsequent action will be documented and reported to the OSU IRB and the Program Officer at NIH. Adverse event reports will be reviewed annually with the OSU IRB to ensure participant safety.

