## **Protocol Amendments/Changes**

Any changes or amendments to the protocol made in response to adverse events/SAEs (or independent of AEs/SAEs) will be requested in writing to the IRB, which will then grant or deny permission to make the requested change in protocol. Approved changes and amendments will be reported to the NIH.

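### Optional safety improvement: repeat the urine pregnancy test before smoking at visits 2 to 4, where no scheduled test now follows visit 1

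*Combined protocol and SAP*

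**What the plan says.** All references are to the combined protocol and SAP.

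- **Visit 1 (section IV).** "Each female participant of child-bearing age will be asked to provide a urine sample" for a dip-stick pregnancy test. A woman who tests negative may take part if she agrees in writing "to use reliable contraception throughout their participation in the study".
- **Visits 2 to 4 (section IV, Safe Departure and Remuneration).** These resemble visit 1, except that "the tobacco and use history data collection and the urine pregnancy test (women only) will not be repeated".
- **Spacing (section IV).** There are four sessions, "each visit separated by at least a week". No maximum interval is given.
- **Exclusions (Table III.4).** Women who are pregnant or suspect it, are trying to conceive, are breastfeeding, or will not use contraception during the study are excluded. The stated reason is that enrolling pregnant or breastfeeding women in smoking research would be unethical.
- **Monitoring (Appendix D, Adverse Events).** Pregnancy is named among the conditions screened for, without a schedule. Adverse events are collected by self-report at follow-up visits.

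**The concern.** Each session supplies 15 g of tobacco, smoked for up to 60 minutes. Section II.2 lists developmental toxicants among what waterpipe smoke can deliver. Two groups of women could pass the single test and still smoke while pregnant at a later visit: those whose pregnancy is too early to show at visit 1, and those who conceive between visits. Either could smoke up to three further study-supplied bowls.

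The signed agreement looks forward from visit 1, so it does not act on conceptions in the days before that visit. The exclusion of women trying to conceive does bear on them.

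The protocol already applies other checks at each session: exhaled CO at or below 10 ppm (section IV) and absence of intoxication (Table III.4). A repeat pregnancy test would fit the same flow.

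**Working it through.** The plan gives no figure to reproduce. The check counts the untested sessions and then sizes the benefit of testing them.

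**Inputs from the documents**
- 60 recruited, 50 complete data sets sought (section III.B3).
- Share of women: 51.3% in the city census, up to 62% in the team's earlier studies (section VIII.1). These are not enrolment targets. All women are treated as of child-bearing age.
- Four sessions at least 7 days apart, so visit 4 is at least 3 × 7 = 21 days after the only test.

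**Assumptions not in the documents**
- Annual pregnancy risk of 1 to 15%, at a constant rate.
- A dip-stick turns positive L = 10 to 14 days after conception.
- No woman recognises and reports a pregnancy without a test.

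**Untested sessions**
- Per woman: 3/4 = 75%.
- 50 completers: 50 × 0.513 = 25.65 to 50 × 0.62 = 31.0 women; × 3 gives about 77 to 93 sessions.
- All 60: 30.78 to 37.2 women; × 3 gives about 92 to 112 sessions.

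**Sessions smoked while pregnant, and the share averted.** Put visit 1 at day 0. Conceptions before day −L are caught at visit 1. A session at day t is smoked while pregnant if conception falls between day −L and day t, a window of t + L days. A test at that visit averts it if conception falls between day −L and day t − L, a window of t days.

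| Gap between visits | Averted (sum of t) | Without repeat tests (sum of t + L) | Share averted |
|---|---|---|---|
| 1 week | 7 + 14 + 21 = 42 | 42 + 3L = 72 to 84 | 58% to 50% |
| 2 weeks | 14 + 28 + 42 = 84 | 114 to 126 | 74% to 67% |
| 4 weeks | 28 + 56 + 84 = 168 | 198 to 210 | 85% to 80% |

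(Ranges run from L = 10 to L = 14.)

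**Where the weekly benefit comes from.** The part due to conceptions before visit 1 is the sum of the smaller of t and L.
- L = 10: 7 + 10 + 10 = 27, and 27/42 = 64%.
- L = 14: 7 + 14 + 14 = 35, and 35/42 = 83%.

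The remaining 15/42 (36%) or 7/42 (17%) comes from conceptions after visit 1. A test at day 7 cannot show any of these when L is 10 or more.

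**Expected numbers, 50 completers, weekly spacing**
- Pregnancies arising in the matching window of 21 + L = 31 to 35 days: 25.65 × 0.01 × 31/365 = 0.022 to 31.0 × 0.15 × 35/365 = 0.45.
- Sessions averted: 25.65 × 0.01 × 42/365 = 0.030 to 31.0 × 0.15 × 42/365 = 0.535.
- Averted sessions scale with the sum of t, so they double at two-week gaps (84/42) and quadruple at four-week gaps (168/42).

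**The case against.** The strongest case against is that the plan makes this choice openly and breaks none of its own rules. Table III.4 justifies the exclusion in terms of enrolment, which the visit-1 test covers. A reader might infer that dropping the test contradicts the exclusion. The documents do not support that, and this part of the objection stands.

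A reader might also infer that the later sessions rest on the visit-1 test alone. They do not: the contraception agreement, the exclusions, and the screening and self-report in Appendix D all remain. The consent pages are not in the public text, so an instruction there to report a suspected pregnancy may exist unseen. What remains is that none of the visible safeguards is a scheduled test, and self-report cannot catch a pregnancy that the woman has not recognised.

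The benefit is small and rests on outside assumptions. Entry requires at least three waterpipe sessions in the past month, so three study sessions over three or more weeks are of the same order as what participants already smoke. That stands and limits the weight of the point, though these sessions are supplied by the study.

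Finally, lighter options exist, such as a scheduled pregnancy question or a retest only after a long gap. At weekly spacing the visit-4 test adds only 7/42 = 17% of the benefit. These options are reasonable. However, a question does not detect unrecognised pregnancy, and retesting only after long gaps would miss the early conceptions that dominate at weekly spacing.

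**Conclusion.** The point holds as an optional, low-cost safety improvement. After visit 1 no scheduled pregnancy test precedes three of the four smoking sessions. At weekly spacing the main gap is a conception too early to show at visit 1 (about 64 to 83% of the benefit). Conceptions between visits matter more if gaps are long, which the protocol does not rule out.

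A reader might take this to mean that an appreciable number of pregnant women would be exposed. The figures do not support that at weekly spacing: about 0.02 to 0.45 pregnancies in the window and about 0.03 to 0.54 sessions averted across 50 completers. They depend on the assumed risk and lag. They would be higher with wider visit gaps and lower if women recognise and report a pregnancy themselves. Repeat tests would still miss conceptions shortly before a visit. The case for change rests on its low cost and on the ethical weight that the protocol itself gives to the exclusion. No estimate or test in the analysis is affected.

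**What to change.** In section IV, under Safe Departure and Remuneration, remove the urine pregnancy test from the items not repeated. At each of visits 2 to 4, repeat the existing dip-stick for women of child-bearing age alongside the CO check and before venipuncture, as at visit 1, and read it before smoking starts. State that a participant who tests positive does not smoke and is withdrawn from further sessions; the visible text has no rule for a pregnancy found after visit 1.

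Cost: about 77 to 93 extra dip-sticks for 50 completers (up to about 112 if all 60 attend every visit), a few minutes per visit and slight participant burden. The documents give no unit price, so calling this cheap is a judgement; the test and the staff are already in place. It also needs a minor amendment, which under Appendix D (Protocol Amendments/Changes) "will be requested in writing to the IRB". Power and alpha are unchanged.
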